## 1.4 Specific Aims

**Aim 1. (Efficacy Primary Endpoint): Evaluation of (-)-epicatechin on blood and muscle tissue markers of mitochondrial biogenesis and muscle regeneration in adults with Becker muscular dystrophy.** Treatment with 8 weeks of (-)-epicatechin 100mg daily will induce mitochondrial biogenesis, muscle regeneration, and improved histological appearance in sarcomere morphology.

*Hypothesis:* (-)-Epicatechin will show evidence of mitochondrial biogenesis by Western blot assays of biceps brachii muscle biopsies through increases in ETC1, ETC5 and SOD2 proteins.

*Hypothesis:* (-)-Epicatechin will show evidence of induction of muscle regeneration through increases in PGC1a, decreases in acetylated (inactive) PGC1a, and increases in follistatin,

myogenin, and MyoD compared to pre-treatment baseline as determined by Western blot assays of biceps brachii muscle biopsies.

*Hypothesis:* Administration of (-)- epicatechin will be associated with increases in plasma concentrations of follistatin, a known hormonal regulator of muscle regeneration and a potential pharmacodynamic biomarker.

*Hypothesis:* Administration of (-)- epicatechin will be associated with electron microscopy evidence of increases in mitochondrial number and cristae density within the mitochondria compared to pre-treatment baseline.

*Hypothesis:* Administration of (-)- epicatechin will be associated with increased nNOS expression in skeletal muscle compared to pre-treatment baseline and this increased expression will be associated with improved muscle perfusion during exercise.

**Aim 2 (Efficacy Secondary Endpoints): Evaluation of the effects of (-)-epicatechin on exercise capacity in adults with Becker muscular dystrophy.** Individuals with Becker muscular dystrophy who receive 100mg/day of (-)-epicatechin will demonstrate improved exercise performance and strength that is associated with increases in mitochondrial biogenesis and muscle regeneration.

*Hypothesis:* Using the 6 minute walk test, and a standardized recumbent cycle exercise test with measurement of lactic acid levels, VO2 max, Work max, anaerobic threshold, and NIRS-defined skeletal muscle perfusion (measures of oxyhemoglobin, deoxyhemoglobin, and tissue saturation index) we will detect pre-/post-treatment differences in exercise capacity and endurance that will be clinically significant ( $\geq 5$ -10%) and reflect increases in mitochondrial biogenesis.

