**Figure 26: Muscle structural proteins induced by (-)-epicatechin-rich cocoa in HF/DM2 patients.**

HF/DM2 patients before (b) and after (a) 30 day treatment with epicatechin-rich cocoa. Muscle control = healthy volunteers. SG: sarcoglycans, DG: dystroglycan

As the perturbation of dystrophin levels can greatly compromise sarcomere organization and thus, contractile function, SkM samples were evaluated using electron microscopy. Figure 27 shows a representative sample from one patient obtained before vs after treatment. As observed, at baseline sarcomere “organization” was very poor (no clear definition of Z and other bands). With treatment, sarcomere organization markedly recovered. Results were “quantified” using blinded, naïve graders and a highly significant improvement ( $P < 0.0001$ ) was observed in sarcomere organization ( $1.7 \pm 0.5$  before vs.  $3.1 \pm 0.5$  after out of a maximum scale of 4) after scoring 100 EM images (10 before, 10 after/patient).

**Figure 27: Changes in sarcomere ultrastructure in representative HF/DM2 patient before and after treatment with (-)-epicatechin-rich cocoa.**

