## 8 ASSESSMENT OF EFFICACY

### 8.1 Laboratory Efficacy Parameters

- Peripheral Blood Tests

Peripheral venous blood will be collected at points specified in the study visit chart to evaluate:

- Creatine phosphokinase (CPK)

- Follistatin
  - mRNA and miRNA biomarker profiles
  - Pharmacokinetics: epicatechin metabolites [serum tested at trough, 2 hours (Tmax), 4 hours after dose at baseline, week 2, week 4 and week 8].
  - Blood lactate testing during exercise: Blood lactate levels will be collected at baseline and 2-minute intervals by finger-stick or ear-stick during 6-minute cycle testing.
- Muscle Biopsy (Biceps Brachii)

Open biopsies of the mid-biceps will be conducted at baseline and after 8 weeks of study medication dosing. The muscle biopsy samples will be collected by open biopsy or according to standard hospital procedures. The minimum amount of muscle tissue required is a small piece of muscle of at least 0.5 x 1.0 x 1.0 cm. If possible, the tissue collected will be of sufficient size to provide 4 (four) pieces of tissue (each 0.5x0.5x0.5cm). Muscle for histological evaluation will be sent fresh to hospital pathology. Muscle tissue for evaluation at outside labs will be immediately frozen in liquid nitrogen-cooled 2-methylbutane and stored at -80°C or -70°C till shipment. Biopsy at baseline will be collected from the lateral aspect of the midpoint of the biceps muscle without the use of depolarizing agents or Bovie catheterization prior to tissue extraction. Biopsy at 8 weeks will be collected from medial aspect of the midpoint of the biceps muscle of the same arm, and must be separated by a margin of at least 1cm to avoid scar tissue from the earlier biopsy.

Histology samples will be evaluated ([name] lab, UC Davis) to examine:

- Fiber size variation
- Tissue necrosis
- Degree of central nucleation
- Presence of basophilic/regenerating fibers
- Fiber type (myosin IHC stains)
- NADH-TR and succinic dehydrogenase (mitochondria)

Muscle biopsy samples will be examined by Western blot ([name] lab, UC San Diego) to evaluate:

Initial Phase (done immediately upon biopsy)

- Muscle regeneration: follistatin, MyoD, myogenin, dystrophin, sarcoglycans, dysferlin
- Oxidation/oxidative stress: SOD1, SOD2, catalase, GSK, nNOS, eNOS
- Mitochondrial function: ETC-I, ETC-V, mitofilin, porin
- Transcriptional regulation: PGC1-alpha
- Collagen deposition: Collagen I, collagen III, fibronectin

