Delayed Phase (completed on stored material at a later date if warranted by initial data)

- Glucose transport: Glut1, Glut 4 (and ratio)
- Apoptosis: cytochrome-c, caspase
- Dystrophin-associated complex (DAP) ([name] lab, University of Iowa): sarcoglycans (alpha, beta, gamma, delta, epsilon), laminin-2 (alpha, beta, gamma), alpha dystrobrevin-2, syntrophin
- Matrix metalloproteinase-9

Muscle biopsy samples will be examined by electron microscopy ([name] lab, UC San Diego) to evaluate:

Initial Phase (done immediately upon biopsy)

- Sarcomeric structure
- Mitochondrial number and localization

Delayed Phase (completed on stored material at a later date if warranted by initial data)

- Myofiber volume
- Mitochondrial volume per myofiber volume

- Mitochondrial cristae density

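### Initial Phase Western blots and EM are to be done as each biopsy is taken, with no rule to run or read a participant's two samples together, so run-to-run assay differences enter the primary pre/post change

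*Combined protocol and SAP*

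**What the plan says.** Aim 1 (section 1.4) is the primary efficacy aim. Its hypotheses are changes from the pre-treatment biopsy, for example in "myogenin, and MyoD compared to pre-treatment baseline as determined by Western blot assays of biceps brachii muscle biopsies". Section 8.1 sets the sampling: "Open biopsies of the mid-biceps will be conducted at baseline and after 8 weeks of study medication dosing".

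The same section splits the Western blot and EM work into two sets. The first is headed "Initial Phase (done immediately upon biopsy", with identical wording for both methods. The second is headed "Delayed Phase (completed on stored material at a later date if warranted by initial data". The Initial Phase holds ETC-I, ETC-V, SOD2, PGC1-alpha, follistatin, MyoD, myogenin and nNOS by Western blot, and sarcomeric structure and mitochondrial number by EM. The Delayed Phase includes "Mitochondrial cristae density", which is also named in an Aim 1 hypothesis.

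On handling, section 8.1 says that tissue for outside laboratories is "immediately frozen in liquid nitrogen-cooled 2-methylbutane and stored at -80°C or -70°C till shipment". It gives no shipping schedule. Neither section 8.1 nor section 11 mentions putting a participant's two samples in one run, a common reference sample, normalisation across runs, or masking of readers to visit.

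**The concern.** The primary quantity is a within-person difference between two assay results. Pairing removes variation between men, but it removes assay variation only when both members of the pair share the run. If the baseline sample is processed before the Week 8 sample exists, differences in gel, transfer, antibody lot, exposure and reader enter each man's change in full. There is no control arm in which the same differences would appear and could be subtracted.

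The study's success criterion (sections 1.3 and 11) is a response magnitude large enough to power a Phase IIB study of 30. Extra variance in the change shrinks the standardised response, so a marker that does respond could be judged unusable for the next trial.

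**Working it through.** **Is the separation really directed?** The contrast between the two phase labels shows that the timing is a stated rule. With biopsies 8 weeks of dosing apart and assay on collection, the two Initial Phase results in a pair are about 8 weeks apart. The Delayed Phase works on stored material, so its pairs can already be run together. The storage sentence sits awkwardly with the word immediately: the Western blot and EM laboratories are at another university, and tissue waits frozen for a shipment with no stated date. The two statements need reconciling.

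**Inputs**
- From the documents: n = 10, one arm; significance level 0.05 (section 11; sidedness not stated, two-sided assumed).
- Assumed, because the documents give no figures: same-run SD of change s = 20% (also 30%); run-to-run CV = 10% to 20%.
- There is no power or assay-precision figure in the plan to reproduce.

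**Step 1. Noise added by separate runs.** Two independent runs add SD = √2 × CV to each man's change:
- CV 10%: 14.1%; CV 20%: 28.3%.
- On the mean of 10, dividing by √10: 4.5% and 8.9%.

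**Step 2. Total SD of change** = √(s² + 2·CV²):
- s = 20%, CV 10%: √(400 + 200) = 24.5%
- s = 20%, CV 20%: √(400 + 800) = 34.6%
- s = 30%, CV 10%: √(900 + 200) = 33.2%
- s = 30%, CV 20%: √(900 + 800) = 41.2%

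**Step 3. Detectable change and power.** For a paired t-test with 9 degrees of freedom, two-sided 0.05 and 80% power, the noncentral t gives a detectable change of 0.996 SD. In the same run this is 19.9% at s = 20% and 29.9% at s = 30%. Power at that same effect, once run noise is added, is:

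| Same-run SD | Run CV | SD of change | Detectable change (80% power) | Power at the same-run detectable effect |
|---|---|---|---|---|
| 20% | 10% | 24.5% | 24.4% | 63% |
| 20% | 20% | 34.6% | 34.5% | 37% |
| 30% | 10% | 33.2% | 33.0% | 72% |
| 30% | 20% | 41.2% | 41.1% | 53% |

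At s = 20% the standardised response is multiplied by 20/24.5 = 0.82 or 20/34.6 = 0.58.

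**Step 4. Noise or bias?** Simulation with no drug effect (50,000 trials per setting) gives a type I error of about 5% when each sample has its own independent run. If instead all baselines shared one run and all Week 8 samples another, type I error at s = 20% would be 38% (CV 10%) or 63% (CV 20%). At s = 30% it would be 24% or 49%. The documents do not describe that second layout. It marks the extreme in which runs line up fully with visit.

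**The case against.** The strongest reply is that the timing label cannot be fully literal. Tissue for outside laboratories is frozen and held for shipment, so the label may only separate assays that are always run from those run "completed on stored material at a later date if warranted by initial data". Paired batching is then not excluded, and gel layout and reader coding may be set out in laboratory procedures outside these documents. This stands as a reason to reconcile the text. It does not remove the problem, because the protocol as written directs early assay and states no safeguard.

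Three stronger readings are tempting, and the documents do not support them.

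- **All of the Western blot and EM work is affected.** It is not. Delayed Phase items, cristae density among them, use stored material.
- **The assays are read unmasked, and masked EM scoring is ruled out.** The protocol is open-label but silent on masking of assay readers. With staggered enrolment, a coded sample arriving at the laboratory could be one man's baseline or another's Week 8. Images taken at each biopsy could also be kept, coded and scored later. The heart failure and diabetes study in section 5.1 reports "using blinded, naïve graders". It does not say that before and after images were scored in one session. The fair statement is that this practice is not carried into section 8.1.
- **False positives are likely.** A common shift of 10, 15 or 20% between visits, with a total SD of change of 20%, would give p < 0.05 with no drug effect in 29%, 56% or 80% of trials. That omits the run noise from step 1. With it, the figures are 21/41/63% (CV 10%) or 13/23/37% (CV 20%). All of them need a shift aligned with visit in all ten men, for which the documents give no evidence.

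It is also fair to say that this is a 10-person pilot judged on response magnitude rather than on a p-value. That makes the SD of change matter more, because the response it reports will be used to plan the next study.

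**Conclusion.** The point holds for the Initial Phase assays, which carry most of the primary Aim 1 markers. As written, paired samples are assayed about 8 weeks apart with no shared run, bridging sample or masked reading required. The dependable harm is added noise. Under an assumed run CV of 10-20%, the SD of change rises from 20% to 24.5-34.6%, and 80% power falls to 63-37% (72-53% at a same-run SD of 30%). These sizes rest wholly on the assumed precision and on independent runs. Bias is conditional on runs or drift lining up with visit, and reading with knowledge of the visit is a possibility left open rather than a stated practice. This is a cheap improvement, best made before any baseline tissue is used.

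**What to change.** In section 8.1, reconcile the Initial Phase timing with the frozen-storage sentence:

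- Preserve and store both Initial Phase samples until the Week 8 biopsy has been taken.
- Run each participant's baseline and Week 8 samples on the same gel and in the same batch.
- Code samples and EM images so that the visit is hidden, and break the code only after densitometry and scoring are locked.

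The cost is protocol and laboratory-manual wording plus sample coding. No extra tissue or visit is needed. The downside is delay: baseline Initial Phase results come at least 8 weeks later, and so does the decision on whether to run the Delayed Phase, so far as it would have used them. No other decision described in the protocol depends on having the baseline results sooner.

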## 8.2 Functional Efficacy Parameters

- Six-Minute Walk Test

Participants will complete the Duchenne muscular dystrophy six-minute walk test (6MWT) as described by McDonald et al [70]. Methods will be adapted for the adult population by removing the element of constant verbal encouragement. Measurements recorded will include 25-meter split times and total distance traveled. During the 6MWT, participants will undergo respiratory gas exchange testing using a Cosmed “backpack” portable metabolic system and muscle perfusion testing using a non-invasive portable near-infrared spectroscopy (NIRS) system.

- Graded exercise test using a recumbent cycle ergometer

Each participant will perform a graded exercise test on an electronically braked recumbent cycle ergometer as previously described [71, 72]. Modifications for Becker muscular dystrophy related proximal weakness will be made as described by others [72, 73]. The exercise test will begin by participants pedaling at a rate of 60 revolutions/min with no load for 1 min (warm up). After the warm-up period, the work rate (WR) on the cycle ergometer will start at 10 W and increase either 10 W/min or every other minute for Becker muscular dystrophy participants until volitional exhaustion. Level of exertion will be monitored by heart rate and the Borg visual analogue scale [74]. Increments will be adjusted so that the duration of the test will be kept between 12 and 15 min. Twelve-lead ECG, blood pressure, O2 consumption ( $\dot{V}O_2$ ), CO2 production ( $\dot{V}CO_2$ ), and ventilation (VMax, SensorMedics/VIASYS Healthcare) will be continuously measured. After volitional exhaustion, participants will be immediately placed in the supine position, where a postexercise ECG will be performed within 15–30 s. Exercise tests will be considered to be maximal if the peak heart rate (HR) is 85% of that predicted for age ( $220 - \text{age}$ ) and/or the peak respiratory exchange ratio (RER;  $\dot{V}CO_2/\dot{V}O_2$ ) is  $\geq 1.15$ . Muscle perfusion testing of a quadriceps muscle will be performed during cycle exercise using a non-invasive portable near-infrared spectroscopy (NIRS) system as described by Allart et al. [75]. We will use a non-invasive three channel, portable continuous-wave NIRS device (PORTAMON, Artinis Medical Systems, Zetten, The Netherlands). Participants will undergo blood lactate testing at baseline and at 2-minute intervals as specified in the “Peripheral Blood Tests” section.

- Quantitative Muscle Testing

Isometric and isokinetic QMT of elbow and knee flexors and extensors will be conducted using the BIODEX ergometer. The highest value of three consecutive maximal strength testing efforts will be recorded. Specific methods for testing can be found in the BIODEX manual of operations. Quantitative hand grip strength will be assessed using the CiTEC handheld ergometer, again recording the highest value of three consecutive tests for each hand. Methods for testing can be found in the CiTEC manual of operations.

- Range of Motion Testing

Passive ranges of motion for knee extension, ankle dorsiflexion, elbow extension and wrist extension will be measured to the nearest 5 degrees using goniometry techniques as described by Pandya et al [76] and Fowler [77]. Knee and elbow extensions ranges from 20 to -150 degrees. Ankle dorsiflexion range is from 20 to -80 degrees, with 0 degrees considered full passive range of motion. Wrist extension with fingers extended range is from 100 to -90 degrees, with 90 degrees considered full range of motion.

- Pulmonary Function Tests

Standard PFTs will be done using the Renaissance II spirometer. Spirometry has been used extensively as a measure of respiratory function. PFTs include maximal inspiratory pressure (MIP), maximal expiratory pressure (MEP), forced vital capacity (FVC), forced expiratory volume 1 (FEV1), peak expiratory flow (PEF), maximum ventilatory volume (MVV) and peak cough expiratory flow (PCEF).

- Timed Function Testing

Timed Function Testing has frequently been used to assess functional abilities in three important areas: rising from the floor, climbing four standard stairs and walking/running 10 meters. Each of these skills is timed to provide a quantitative measure of function. Specific methods are outlined in Florence et al [78].

- **Functional Evaluation**

The functional classification used by CINRG utilizes a scale modified from the upper extremity scale reported by Brooke et al [79] and the lower extremity scales used by Vignos et al [80]. The functional grades consist of six levels of function for the upper extremities and eleven levels for the lower extremities. Specific methods are outlined in the CQMS User's Manual.

- **Anthropometric Measurements**

Standing height will be measured to the nearest 0.1cm in all participants. Weight will be measured to the nearest 0.1kg. Waist and hip circumference will be measured to the nearest 0.1cm and waist-hip ratio will be calculated.

- **Body Composition Assessment by Dual energy X-ray absorptiometry (DEXA) (15 minutes):**

DEXA scans are primarily used to evaluate bone mineral density. It can also be used to measure total body composition and fat content with a high degree of accuracy. For this study it will be used to measure total and regional body composition. DEXA uses X-rays to assess bone mineral density or measure total body composition. However, the radiation dose is approximately 1/10th that of a standard chest X-ray. Bone density will be evaluated based on whole-body and subcranial total bone mass and areal bone mass (adjusted mass for bone size).

- **Multifrequency Bioimpedance Assessment (MFBIA)**

Participants will undergo multifrequency bioimpedance assessment (MFBIA) testing using a Xitron model 4000 MFBIA system to painlessly and non-invasively assess the amount of total body water, intracellular water, extracellular water and fat-free mass. One electrode is placed to bisect the ulnar head, and the other electrode is placed just behind the middle finger. On the ankle, one electrode is placed to bisect the medial malleolus, and the other electrode is placed just behind the middle toe. Impedance is measured between upper and lower extremity electrodes.

- **Upper Extremity Range of Motion Testing (20 minutes)**

Upper Extremity Range of Motion Testing (20 minutes). The subject will be asked to perform the following range of motion activities while wearing the Cal-FIT physical activity motion analysis system and recorded by the stereo-camera optical measurement system:

1. move their elbow through a complete range of motion from maximally flexed to maximal extension
2. move the forearm through a complete range of motion from maximal pronation to maximal supination
3. move the wrist through a complete range of motion from maximal extension (dorsiflexion) to maximal flexion (palmar flexion) and from radial deviation through ulnar deviation
4. move the shoulder through a complete range of motion from maximal extension to maximal flexion, maximal abduction to maximal adduction, and from maximal internal rotation to maximal external rotation.

While being monitored by a motion sensing system (KINECT):

1. perform a series of standardized range of motion and functional upper extremity tasks
2. perform a series of standardized range of motion and functional upper extremity tasks while holding a weight

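### The 12–15 minute rule for the graded cycle test does not hold the ramp constant within a participant, so cycle outcomes before and after treatment may not be comparable

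*Combined protocol and SAP*

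**What the plan says.** Section 8.2 describes a recumbent cycle test with a warm-up of "pedaling at a rate of 60 revolutions/min with no load for 1 min (warm up". The work rate will then "start at 10 W and increase either 10 W/min or every other minute for Becker muscular dystrophy participants until volitional exhaustion". The next rule on the ramp is "Increments will be adjusted so that the duration of the test will be kept between 12 and 15 min". Lactate is sampled at rest and every two minutes, and NIRS is recorded from a quadriceps muscle during cycling.

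Table 3 places the test at Baseline, Week 4, Week 8 and early withdrawal. It shows no functional assessment at screening. Section 6.1.2 (a reproducibility check at screening) and Section 11 (test-retest reliability from screening and baseline) imply some repeat testing, but neither names the cycle test.

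Aim 2 in Section 1.4 lists, for this test, "measurement of lactic acid levels, VO 2 max, Work max, anaerobic threshold, and NIRS-defined skeletal muscle perfusion", and expects "pre-/post-treatment differences in exercise capacity and endurance" of at least 5–10%. Cycling time is not a listed measure. Section 1.3 calls the test standardized. Section 8.1 places the lactate sampling in a 6-minute cycle test, which does not agree with the 12–15 minutes in Section 8.2.

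**The concern.** A rule that targets duration lets the work-rate ramp vary. That is harmless if the ramp is chosen once per person. It is not harmless if the ramp may be reset at each visit, because the visits are then different tests. The protocol does not say which is meant, and it gives staff two reasons to change the ramp later: the first test may miss the window, or performance may move out of it.

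The stakes lie in the design. The study is single-arm with ten participants, so no control group would absorb a shift caused by the test procedure. Under Section 11, one biologic, strength or performance measure with a large enough response can meet the success criterion and support a 30-person study. A change of ramp could produce or hide a difference of the size sought in a time-indexed measure.

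**Working it through.** The documents give no calculation for this test, so there is no figure to reproduce.

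**Inputs.** From Section 8.2: start at 10 W, steps of 10 W every s minutes (s = 1 or 2), window 12–15 min. From Section 1.4: gain sought g = 5–10%. It is not stated whether the 1-minute warm-up counts in the window; the main case excludes it.

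**1. Which peaks fit the window?** With time in the last stage pro-rated, peak work rate is W = 10 × t / s.
- s = 1: 10 × 12 to 10 × 15 = 120–150 W.
- s = 2: 10 × 12/2 to 10 × 15/2 = 60–75 W. At 15 min the stage in progress is 80 W, hence 60–80 W by stage.
- Counting the warm-up (loaded time 11–14 min): 110–140 W and 55–70 W.
- A 100 W participant lasts 10 min on 1-minute steps and 20 min on 2-minute steps. Neither fits.

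**2. When does a gain leave the window on an unchanged ramp?** Duration becomes t(1 + g), which exceeds 15 min only if t > 15/(1 + g).
- g = 5%: 15/1.05 = 14.29 min; (15 − 14.29)/3 = 24% of the window's width.
- g = 10%: 15/1.10 = 13.64 min; (15 − 13.64)/3 = 45%.
- Counting the warm-up: 22% and 42%.
- From 12 min, a gain of up to 15/12 − 1 = 25% stays inside.

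These are shares of the window. They equal shares of participants only if baseline times are uniform, which is an assumption.

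Once a participant does leave the window, the listed steps may not bring the test back. At 72.5 W (2-minute steps, 14.5 min), a 5–10% gain gives 15.2–16.0 min. Moving to 1-minute steps gives 7.6–8.0 min.

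**3. What does a changed ramp do?** Take 145 W reached in 14.5 min, then a true 10% gain to 159.5 W on a ramp set to end at 13.5 min.
- New ramp: 159.5/13.5 = 11.8 W/min.
- Duration: 13.5/14.5 − 1 = −6.9%. Work max: 159.5/145 − 1 = +10%.
- Load at minute 6: 10 × 6 = 60 W before, 11.8 × 6 ≈ 71 W after, about 18% higher. Between the two listed ramps the contrast is 60 W against 30 W.

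So duration misleads and readings at the same minute are not like for like, while Work max still shows the gain unless the ramp itself shifts it. The documents give no such shift b. As assumed values, the observed gain is (1 + g)(1 ± b) − 1:

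| Assumed b | True +5%: shift down / up | True +10%: shift down / up |
|---|---|---|
| 0% | +5.0% / +5.0% | +10.0% / +10.0% |
| 2% | +2.9% / +7.1% | +7.8% / +12.2% |
| 5% | −0.3% / +10.3% | +4.5% / +15.5% |
| 10% | −5.5% / +15.5% | −1.0% / +21.0% |

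**4. How coarse is one step?** 10/150 to 10/120 = 6.7–8.3% on 1-minute steps; 10/80 to 10/60 = 12.5–16.7% on 2-minute steps. The first lies inside the 5–10% target, the second above it.

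**The case against.** The strongest reply is that the sentence can be read as fitting the increment to each participant's capacity once. It follows directly on the offer of slower steps for this disease, the test is called standardized, and the method is taken from cited papers that are not available here. An intermediate increment chosen in advance is not ad hoc. This stands as a possible reading, and it is why the finding is an ambiguity and not a stated error. It does not close the gap: no section limits the rule to Baseline.

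A reader might infer that any improvement triggers a new ramp and so masks the gain sought. The documents do not support that. No section says that improvement triggers a new ramp, and a 5–10% gain often stays inside the window. Duration is not a named outcome, although the Aim speaks of endurance. The test runs to exhaustion, so the window caps neither Work max nor VO2 max. The direction of any ramp effect on Work max is unknown and could inflate the gain.

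It can also be said that the protocol does not commit to comparing lactate or NIRS by clock minute, and that the ergometer sets the work rate, so matched comparison remains possible where loads overlap. That is right, but the protocol does not call for a matched comparison either. Finally, this is a small pilot that counts validation of the cycle test among its own aims. That limits the consequences, but such validation also needs the same test at each visit.

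**Conclusion.** The concern holds in a limited form. The duration rule leaves open whether a participant's ramp may change between Baseline, Week 4 and Week 8. With steps that fit only about 120–150 W or 60–80 W, and no cycle test scheduled before Baseline, a change is plausible for participants outside those ranges or near the edge of the window. If it happens, time-indexed lactate and NIRS readings are taken at different loads (about 18% apart in the example), and Work max may move either way by an amount the documents cannot settle. Separately, a 10 W step is coarse against a 5–10% target, clearly so on 2-minute steps, and Work max is not defined for an unfinished stage.

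This rests on work rate rising in proportion to loaded time. How many participants would be affected cannot be estimated, because the documents give no peak work rates for this population.

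**What to change.** In Section 8.2:
- State that the increment is chosen once per participant at Baseline, and that the identical ramp is used at Weeks 4 and 8 even if the test then falls outside 12–15 min.
- Record the ramp used at every test.
- Define Work max as the last completed stage plus the participant's own increment times the fraction of the final stage completed. A fixed 10 W would be wrong for anyone given another increment.
- Compare lactate and NIRS before and after treatment at matched work rates.

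Reconcile the 6-minute cycle test in Section 8.1 with the 12–15 minute test in Section 8.2.

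The cost is protocol wording. For a participant whose Baseline test was inside the window, a 5% gain runs to at most 15 × 1.05 = 15.75 min and a 10% gain to 15 × 1.10 = 16.5 min, an overrun of 0.75 or 1.5 min. Participants whose Baseline test missed the window will miss it again. That is the price of keeping the visits comparable.

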##### Participant Exclusion Criteria

- Currently enrolled in another treatment clinical trial.
- History of significant concomitant illness or significant impairment of renal or hepatic function.
- Use of regular daily aspirin or other medication with antiplatelet effects within 3 weeks of first dose of study medication.
- Regular participation in vigorous exercise.
- Symptomatic heart failure with cardiac ejection fraction <25%

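### A pre/post rise in VO2 max or Work max can reflect a harder try at Week 8, because the plan never matches effort between visits

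*Combined protocol and SAP*

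**What the plan says.** Section 8.2 describes a graded recumbent cycle test. After a warm-up the load starts at 10 W and will "increase either 10 W/min or every other minute for Becker muscular dystrophy participants until volitional exhaustion". The increments are adjusted so that the test lasts 12 to 15 minutes. On monitoring it says: "Level of exertion will be monitored by heart rate and the Borg visual analogue scale". On validity it says: "Exercise tests will be considered to be maximal if the peak heart rate (HR) is 85% of that predicted for age", with predicted heart rate taken as 220 minus age, "and/or the peak respiratory exchange ratio" is at least 1.15. Either limb alone is therefore enough.

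Aim 2 in Section 1.4 takes VO2 max, Work max, anaerobic threshold, lactate and NIRS measures from this test and the six-minute walk, and states that "we will detect pre-/post-treatment differences in exercise capacity and endurance that will be clinically significant", at 5-10% or more, reflecting mitochondrial biogenesis.

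Sections 1.3 and 11 call the trial a success if at least one biologic, strength or performance measure shows a response large enough to power a Phase IIB study of 30 people. Section 1.3 describes an open-label study of 10 adults at one center, and Section 6.1.3 says there is no randomization. Table 3 places the cycle test at Baseline, Week 4, Week 8 and early withdrawal, but not at Screening.

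**The concern.** Peak VO2 and peak work depend on how hard the participant pushes. He decides when to stop, he knows he is on treatment, and he may expect to do better at Week 8. There is no control arm to show how much peak values drift without the drug.

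Nothing else in the plan separates effort from capacity. No section requires a VO2 plateau, both limbs of the definition, the same limb at both visits, or similar peak heart rate, RER or Borg rating within a pair. No section says what happens to a test that meets neither limb. No repeat cycle test is scheduled before dosing, although Section 11 plans a reliability coefficient from screening and baseline measures. The 15% reproducibility requirement in Section 6.1.2 names no test and is wider than the 5-10% gain sought.

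At stake is the main decision of the pilot. An effort gain in one peak measure could satisfy the success criterion and also make 30 people look sufficient for the next trial when they are not.

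**Working it through.** The plan gives no VO2, resting heart rate or power figure for this test, so there is nothing of its own to reproduce. The check asks how wide a range of effort the word maximal can cover.

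**Inputs from the protocol.** Threshold 0.85 × (220 − age) and RER alternative (Section 8.2); ages 18 to 60 (Section 6.1.1); 5-10% gain sought (Section 1.4); 10 participants (Section 1.3).

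**Assumptions, not in the protocol.** Resting heart rate 70; resting VO2 3.5 and peak VO2 20 ml/kg/min; true maximal heart rate equal to 220 − age; VO2 rising in a straight line with heart rate from rest to maximum.

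**Formulas.**
- Fraction of reserve at threshold: f = (0.85 × (220 − age) − 70) / ((220 − age) − 70).
- Total VO2 at threshold: V = 3.5 + f × (20 − 3.5).
- Largest gap between two tests labelled maximal: 20 / V − 1.
- VO2 per beat: s = 16.5 / ((220 − age) − 70). Extra beats for +5%: 0.05 × V / s; for +10%: 0.10 × V / s.

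| Age | Predicted maximum | 85% threshold | f | V | Largest gap | Beats for +5% | Beats for +10% |
|---|---|---|---|---|---|---|---|
| 18 | 202 | 171.7 | 101.7/132 = 0.770 | 16.21 | 23.4% | 6.5 | 13.0 |
| 40 | 180 | 153.0 | 83/110 = 0.755 | 15.95 | 25.4% | 5.3 | 10.6 |
| 60 | 160 | 136.0 | 66/90 = 0.733 | 15.60 | 28.2% | 4.3 | 8.5 |

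For age 40 in full: V = 3.5 + 0.7545 × 16.5 = 15.95; s = 16.5/110 = 0.15 per beat; 0.05 × 15.95 / 0.15 = 5.3 and 0.10 × 15.95 / 0.15 = 10.6.

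**Sensitivity.** With resting heart rate 60 to 80 and peak VO2 15 to 30, the gap runs from 19.6% to 36.1%. The extra beats run from 3.3 to 7.7 for +5% and from 6.7 to 15.5 for +10%. If VO2 is simply proportional to heart rate, the gap is 1/0.85 − 1 = 17.6%.

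**Effect on the group mean.** If a man who moves from the threshold to his maximum gains about 25% and the others do not change, a mean gain of 5% needs 10 × 5/25 = 2 men and a mean gain of 10% needs 10 × 10/25 = 4 men, with no drug effect.

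**Work max.** Suppose it is the last completed 10 W stage, which Section 8.2 does not specify. At 10 W per minute, a test of 12 to 15 minutes ends at 120 to 150 W, and one more stage adds 8.3% to 6.7%. At 10 W every other minute it ends at 60 to 70 W, and one more stage adds 16.7% to 14.3%.

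**The case against.** The strongest reply is that the 85% figure is a label and not a stopping rule. Every test runs to exhaustion, and no analysis in Section 11 uses the label to include, exclude or adjust a value. That is right. A reader might infer that the 85% rule itself causes the bias or lets participants stop early, and the text does not support this. The source is effort-dependent testing without blinding or control, as it also is for grip, isometric strength, MIP, MEP and the six-minute walk. The label simply does nothing to limit it. Running to exhaustion also narrows the real range, so the gaps above are ceilings.

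A reader might also infer that the rule wrongly fails men who give full effort but cannot reach 85%, since the heart-failure exclusion reads only "Symptomatic heart failure with cardiac ejection fraction <25"% and rate-limiting drugs are not excluded. Such men can still qualify on RER, and Section 6.1.1 also excludes significant concomitant illness. This reading is largely answered by the definition itself.

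A third tempting step is to divide the reserve fractions directly: at age 40, 1/0.755 gives 33%, with about 4 and 8 beats for +5% and +10%. Those figures apply to VO2 above rest. Aim 2 measures total VO2, for which 25% and about 5 and 11 beats apply.

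It is also fair to say that these are secondary endpoints, that Section 1.2 presents the cycle test partly as endpoint development, and that heart rate, Borg rating, gas exchange and lactate are all recorded. Effort could be inspected. What remains is that no rule requires it, while the success criterion can rest on a peak value alone.

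**Conclusion.** The point holds as a cheap improvement to secondary endpoints. The plan cannot tell a harder effort from a gain in capacity when it reads a pre/post change in VO2 max or Work max, and it lets either one alone decide success.

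The size, about 23-28% in total VO2 across ages 18 to 60, is an upper bound resting on the assumptions listed above. The protocol gives no data to show how often participants would stop near the threshold. The more telling result is how small a shift is enough: a few beats at peak covers the whole effect sought.

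The documents do not support making RER of at least 1.15 compulsory and dropping the other pairs. RER is also only a floor: peaks of 1.15 at Baseline and 1.30 at Week 8 would both qualify at different effort. With 10 men, dropping pairs would also select on a post-treatment metabolic variable in a trial that hypothesizes a mitochondrial effect.

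**What to change.** Amend Section 8.2 and Aim 2, with a matching line on the success criterion in Sections 1.3 and 11:

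1. Call the value VO2 peak, keep all pairs in the main analysis, and report peak heart rate, RER and Borg rating beside it at each visit.
2. Add a sensitivity analysis limited to pairs in which both tests meet the same criterion, including one based on RER of at least 1.15.
3. Do not let a gain in peak VO2 or peak work alone count as the success measure. Rest the exercise-capacity conclusion on anaerobic threshold and on VO2, heart rate and lactate at the same absolute work rate. These depend less on final effort, though they do not replace a control arm.
4. For that comparison, use the same work-rate increments for each participant at every visit. Section 8.2 allows two rates and adjustment, and does not fix them across visits. Reconcile the six-minute cycle test named for lactate sampling in Section 8.1 with the 12-15 minute graded test in Section 8.2.

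All the signals are already planned, so the cost is wording and a little more analysis. The downsides are that fixed increments may take a Week 8 test outside 12 to 15 minutes, and that the effort-matched subset may be only a few pairs.
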